### **Interventional study**

We will conduct a preliminary interventional study, where patients will be randomised to either intensive monitoring/treatment modification, where patients are closely followed up by the research nurse, or conventional therapy following local protocols. Individuals in the interventional part of the study will be:

[figure not shown]
- i) Regularly contacted by the research nurse as detailed below.
- ii) Encouraged to check their glucose levels as appropriate, at least twice a day or more frequently as necessary.
- iii) Special leaflets regarding different aspects of diabetes will be given to patients and will be discussed. These will include leaflets for alcohol, exercise, Carbohydrate counting and awareness as appropriate (please see below).
- iv) Patients will have a dedicated phone number that they can ring for urgent advice.
- v) There will be a dedicated email line set up to answer less urgent queries and help with patient support. An email system is already set up in Leeds by the PI, and patients using this service experienced significant improvement in diabetes control (data not shown).

The research nurse will make every attempt to establish the cause of severe hypoglycemia by taking a detailed medical history in order to clarify clinical comorbidities and assess social circumstances including alcohol intake, patient independence and help provided by carers. The nurse will also document current medications with special attention to dose and frequency of hypoglycemic agents, including insulin. Routine blood tests to assess overall glycemic control, renal and liver function will be performed, which may further help to shed light on the cause of low blood glucose. Hypoglycemic treatment may be changed in cases of concern but only after review by the PI, and the medical team in charge of the patient will be informed. For example, a sulphonylurea may be stopped or replaced if deemed inappropriate for the patient and insulin regimens/doses may also be altered. Follow up of patients after changes to medical therapy are detailed below but some may have more frequent contact with the nurse as per clinical need. The nurse employed will have extensive experience in the management of diabetes and will have the necessary knowledge to adjust doses/mixtures/intervals of insulin as appropriate, with adequate support provided by the PI in difficult clinical scenarios. Other diabetes disciplines, such

as dietitian support may be sought if the research nurse and/or PI find this to be necessary. In cases of newly diagnosed (or suspected) clinical conditions, referrals to an appropriate specialty will be made after review by the PI. If social circumstances are found to be inappropriate, for example in the case of older individuals not managing on their own, the physician in charge of the patient will be informed and steps will be taken to provide support according to the need of each individual.

In summary, the research nurse will concentrate on establishing the cause of the severe hypoglycemic episode and together with the PI will alter treatment, involve other diabetes/non-diabetes disciplines as appropriate and introduce changes to social support as required.

The research nurse will contact the patient weekly for the first month, every two weeks for the following month followed by contact at months 3, 6 and 12. Face to face contact with the patient will be arranged at enrolment, 1, 3 and 12 months. Patient will be asked to fill in the questionnaire at enrolment and end of 3rd month, with selected patients asked to complete the form again at 12 months (explained in Figure 4). Blood tests will be arranged as detailed above. In the standard arm, patient will be contacted only once as per current arrangement and subsequent treatment left to the discretion of the attending physician (summarised in Figure 4).

**Figure 4.** Summary of the preliminary interventional part of the study. U&Es: urea and electrolytes, LFTs: liver function tests, UACR: urinary albumin/creatinine ratio, MACE: major adverse cardiovascular events, m:

month, d: day. Questionnaire will be done at enrolment and 3 months in both groups. If a significant difference exists between the two time points in the same patient, the questionnaire will be repeated at 12 months. Clinical outcome at 12 months will also include frequency of hypoglycemia, analysed separately.

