### **Aims**

The proposed work is divided into two parts through an observational and an interventional study.

1. Observational study: characterise individuals with severe hypoglycemia.
2. Interventional preliminary study: investigate the effect of regular glucose monitoring and specialist nurse input into a) future hypoglycemic events, b) confidence with diabetes management/quality of life and c) clinical outcome.

[figure not shown]

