### **Plan of investigation**

We have already developed a pathway for ambulance services to report cases of severe hypoglycemia in Leeds requiring their intervention (Figure 2).

**Figure 2.** A summary of the current severe hypoglycemia pathway in Leeds. YAS: Yorkshire Ambulance Services, DNS: Diabetes Nurse Specialist, GP: General Practitioner.

We will continue to follow this pathway but will have a dedicated nurse to deal with the patients and will extend the study to include Sheffield. Inclusion of Sheffield will help to boost the number of patients enrolled and will clarify any potential regional variability. The research nurse will be experienced in managing individuals with diabetes and will be conducting both parts of the study, under the supervision of the principal investigator. The proposed study is summarised in Figure 3 and further detailed below.

**Figure 3.** Summary of study design, including both observational and interventional parts. Intensive nursing support and standard clinical care are explained in more detail below.

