### Observational study

Various details will be collected to elucidate the characteristics of patients undergoing severe hypoglycemia requiring emergency services intervention.

**Demographic and general data.** Address, age, sex, type of diabetes and duration, weight, body mass index, blood pressure, presence of macrovascular and microvascular complications, current treatment, status at home (living alone), driving status, alcohol consumption, smoking history, mobility, non-diabetes related co-morbidities. We will also clarify who made the ambulance call (patient/carer/other).

**Patient questionnaire (see appendix 1).** This will address whether a patient feels confident regarding managing his/her diabetes, how often glucose is monitored, can the patient adjust insulin, does the patient understand the dangers of hypoglycemia, presence of hypoglycemia awareness, frequency of low glucose levels, treatment options of hypoglycemia.

**Examination.** Check injection sites for lipoatrophy or lipohypertrophy and examine for signs of peripheral neuropathy (monofilament test).

**Blood and urine tests.** These will be arranged as part of routine clinical care in both groups, unless recent blood tests have been done. The following tests will be included: HbA1c, urea and electrolytes, liver function tests, full lipid profile, thyroid function tests (where appropriate), urinary albumin/creatinine ratio (ACR). HbA1c will be measured every 3 months, U&Es, LFTs and lipid profile 6 monthly. ACR will be checked at enrolment and at 12 months. All above tests will be requested more frequently if clinically indicated.

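### Aim 2a compares hypoglycemia between arms that differ by design in nurse contact and self-testing; the continuing ambulance pathway should be made its source and the count analysed per time alive

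*Combined protocol and SAP*

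**What the plan says.** The Aims section sets the interventional study to "investigate the effect of regular glucose monitoring and specialist nurse input into a) future hypoglycemic events", followed by confidence and quality of life, and clinical outcome. The Figure 4 legend adds hypoglycemia frequency to the 12-month outcomes, to be analysed separately. The Hypothesis section names the target as the risk of severe hypoglycemia.

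The Interventional study section sets different follow-up for the two arms.

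- **Intensive arm:** nurse contact weekly for a month, fortnightly for the next month, then at months 3, 6 and 12. Patients are "Encouraged to check their glucose levels as appropriate, at least twice a day or more frequently as necessary". There is an email line, and "Patients will have a dedicated phone number that they can ring for urgent advice".
- **Standard arm:** "In the standard arm, patient will be contacted only once as per current arrangement".

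Three elements are common to both arms.

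- **Questionnaire:** it is given at enrolment and month 3 in both groups. It is repeated at month 12 only where a patient's answers changed significantly between those two times.
- **Blood and urine tests:** "These will be arranged as part of routine clinical care in both groups".
- **Ambulance reporting:** the Plan of investigation says "We have already developed a pathway for ambulance services to report cases of severe hypoglycemia in Leeds requiring their intervention", then "We will continue to follow this pathway", and that the investigators "will extend the study to include Sheffield".

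The Statistical analysis section offers the t-test, Mann-Whitney and 2x2 tables for between-group comparisons. It does not discuss hypoglycemia as a between-arm outcome.

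**The concern.** The differences in contact and self-testing are the intervention and are legitimate. For that reason the outcome needs a source that does not run through them. If episodes are counted from whatever each arm happens to report, the opportunity to record one differs by arm under the plan's own rules. A difference in hypoglycemia, or the lack of one, could then not be separated from a difference in detection.

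The direction cannot be predicted. More testing and contact can add recorded low readings in the intensive arm, and unblinded self-report can act either way.

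**Working it through.** **Plan's own figure.** There is none for aim 2a. The 200 per arm in the Statistical analysis section is derived for mortality and is taken here as given.

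**Contacts.** Intensive arm after enrolment: 4 weekly + 2 fortnightly + 3 (months 3, 6, 12) = 9. The standard arm has one stated contact, which may itself be the enrolment contact. The month-3 questionnaire in both groups implies at least one further approach, so the two statements need reconciling.

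**Sources in the visible text, side by side.**

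- *Nurse contacts, phone and email lines:* scheduled or offered as part of the intensive arm, so unequal by design.
- *Meter readings:* frequent testing is encouraged in one arm only.
- *Questionnaire, frequency item:* defined by glucose below 3.6 mmol/l, so it depends on testing.
- *Questionnaire, assisted-attack item:* a 12-month recall. At month 3 it covers 9 months before randomisation and 3 after. For a count, the apparent ratio is 0.75 + 0.25 x true ratio, so a true 0.5 shows as 0.875. The answers are banded, so this shows the dilution and does not predict the result.
- *Questionnaire at month 12:* given only to patients selected on a change after randomisation, so not a randomised comparison.
- *Blood and urine tests:* in both groups, but they do not count episodes.
- *Ambulance pathway:* continues during the study, is largely independent of nurse contact and self-testing, and matches the stated target of severe events.

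**Can an ambulance count work with 200 per arm?** Inputs are the 856 patients and over 200 recurrers (Background) and the 1307 events (Figure 1 legend). I assume they describe one series; its length is not documented.

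- Recurrent events per patient: (1307 - 856)/856 = 0.527.
- Proportion with any recurrence: 200/856 = 0.234.
- Negative binomial shape k from (1 + 0.527/k)^(-k) = 1 - 0.234 = 0.766: k = 0.215, which is strong clustering.

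Simulation: 200 per arm, exponential deaths at 17% and 10% in the year, two-sided 5% level. The negative binomial likelihood-ratio test with log time-alive offset is compared with Mann-Whitney on raw counts.

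| Assumed rate per patient-year | True ratio | Negative binomial | Mann-Whitney |
|---|---|---|---|
| 0.527 (k 0.215) | 0.5 | 68% | 46% |
| 0.527 (k 0.215) | 0.7 | 24% | 14% |

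These are from 500 runs. Runs of 1,000 gave 70% and 26% to 27% for the negative binomial, which is within simulation error. Type I error was near 5% for both tests.

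A yes/no table does not recover the loss. With this clustering, a halved rate lowers the proportion with any event only from 0.234 to 1 - (1 + 0.2635/0.215)^(-0.215) = 0.158. Ignoring deaths, the pooled standard error is sqrt(2 x 0.196 x 0.804/200) = 0.0397, so z = 0.076/0.0397 = 1.91, or about 48% power.

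**Range of rates.** If the series covered one year with uniform entry, patients averaged half a year after their first event. The rate is then 2 x 0.527 = 1.05 and the refitted k is 0.28; power is about 84% to 87% for a halving and 37% for a ratio of 0.7. At half of 0.527, power is about 55% and 20% to 22%.

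**Time alive.** Mean years alive = p/(-ln(1 - p)): 0.912 at p = 0.17 and 0.949 at p = 0.10. The ratio is 0.949/0.912 = 1.04, so raw counts shift by about 4% against the intensive arm.

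**Call diversion.** Suppose the intensive-only urgent line diverted 10% or 20% of ambulance calls (assumed) with no true effect. The ratio would show as 0.90 or 0.80. At the 0.527 rate, a false significant benefit would occur in about 6% or 12% to 14% of trials, against a nominal 2.5%.

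**The case against.** **The figures are missing.** Figures 2 to 4 carry the pathway, the design and the follow-up schedule, and one of them may name the source. This stands. The documents do not support the inference that the plan has no common source for aim 2a. They support only that the visible text assigns none.

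**The ambulance count may already be intended.** The Background counts recurrent emergency events, the Hypothesis targets severe hypoglycemia, and the pathway continues. That is a fair reading and makes the fix cheap. It does not exclude nurse- or meter-reported episodes from a frequency of hypoglycemia that carries no severity limit.

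**The questionnaire problems are hypothetical.** A reader might infer that the questionnaire is the measure of aim 2a; no section says so. It is also kept from the research nurse (Appendix 1), which reduces one source of influence but not the dependence on testing, the look-back or the month-12 selection. Those problems matter only if an item is compared between arms.

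**Nine against one is not like for like.** Accepted: the standard-arm contact may be the enrolment contact. The arms still differ by stated rule.

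**Time alive is a weak reason to change the test.** Accepted. The shift is about 4% and Mann-Whitney keeps its type I error. The case for the count model is power.

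**The fix has its own bias.** Diversion by the urgent line could favour the intensive arm. This stands as a limitation. Adding line-managed events in the intensive arm alone would not cure it, because that brings back unequal ascertainment.

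**Conclusion.** The concern holds in a limited form. Counts of hypoglycemia that pass through nurse contacts, the lines or meters are not comparable between these arms, and the month-12 questionnaire as planned is not a randomised comparison. The ambulance pathway is the one described source that largely avoids both problems.

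A reader might go further and infer that the hypoglycemia result is biased in a known direction, or that the trial's main result is compromised. The documents support neither: the direction is uncertain, and mortality, on which the sample size rests, is not affected.

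The recommended analysis gains about 22 percentage points of power for a halving (68% against 46%) and 10 for a ratio of 0.7 (24% against 14%) at the assumed 0.527 rate and shape 0.215. Because the series length is undocumented, its power should be quoted as a range: about 55% to 87% for a halving and 20% to 37% for a ratio of 0.7. Moderate effects would probably be missed. This should be changed, but it does not threaten the study as a whole.

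**What to change.** 1. State that the between-arm measure for aim 2a is ambulance-attended severe hypoglycemia in the 12 months from randomisation, extracted in the same way for all randomised patients in Leeds and Sheffield. Report nurse-, line- and meter-reported episodes descriptively.
2. Analyse the count by negative binomial regression with log time alive as offset, in place of Mann-Whitney on counts.
3. If any questionnaire hypoglycemia item is compared between arms at 12 months, give the form to all survivors in both arms. Do not use the month-3 answer to the 12-month recall item as an effect measure.
4. Reconcile the single standard-arm contact with the month-3 questionnaire in both groups.
5. State possible diversion of ambulance calls by the intensive-only urgent line as a limitation.

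**Cost.** Protocol wording and one record extract. The extract must be arranged for Sheffield, since only a Leeds pathway is described. The comparison narrows to severe events. Extra month-12 forms are needed only if item 3 applies.

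### The 12-month questionnaire goes only to patients whose own answers changed by month 3, so it cannot support a between-arm or durability statement on confidence or quality of life

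*Combined protocol and SAP*

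**What the plan says.** Aims lists "confidence with diabetes management/quality of life" as outcome (b) of the interventional study and gives it no time point. The Figure 4 legend (Interventional study) says: "Questionnaire will be done at enrolment and 3 months in both groups". It then adds: "If a significant difference exists between the two time points in the same patient, the questionnaire will be repeated at 12 months". The main text of the same section agrees, "with selected patients asked to complete the form again at 12 months", and refers to Figure 4 for the explanation.

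Appendix 1 holds the form: 15 separate five-option items, one of them for insulin users only, with no total score. Option 1 is generally the favourable answer. Its title says that the research nurse will not see the form.

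On visits, the research nurse's schedule reads "Face to face contact with the patient will be arranged at enrolment, 1, 3 and 12 months", while "In the standard arm, patient will be contacted only once as per current arrangement". Statistical analysis names unpaired t-tests, Mann-Whitney tests and 2x2 tables for comparing groups. It says nothing about patients who are not asked at 12 months.

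**The concern.** The rule works patient by patient: the words on selection, and on two time points in one patient, exclude the reading that a group-level result triggers a repeat for everyone. Selection is thus on a change that happens after randomisation, in the outcome itself. If the intervention shifts answers by month 3, the arms send different shares and different kinds of patient on to month 12, and randomisation no longer protects the comparison. The missing data are created by design, so better follow-up cannot recover them.

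The natural use of a repeat form is to see whether an early change lasts, so the risk is practical. Depending on the trigger and the analysis, a vanished effect could look sustained, or a real one could be understated. If only improvers are re-measured, they tend to be patients with unfavourable answers at enrolment, and part of their gain from enrolment to month 12 would be regression to the mean.

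**Working it through.** The plan gives no figure for the questionnaire, so there is none to reproduce. The check asks how large a false difference the rule could create. Every value in step 1 is an assumption.

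**1. Inputs.** Normal summary score, SD 1, scored so that higher is better (the reverse of the form's option numbers). Month-3 effect 0.4 SD; true 12-month effect zero. Correlations enrolment-3, enrolment-12 and 3-12 are either 0.6/0.6/0.6 or 0.6/0.5/0.7. Trigger t from 0.5 to 1.75 SD on the change D from enrolment to month 3.

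**2. Distribution of D.** Variance = 2(1 - 0.6) = 0.8, so s = 0.894. The upper trigger is 1.96 x 0.894 = 1.75, a two-sided 5% rule for one patient's change. With arm mean d (0 standard, 0.4 intensive):
- improvers only: p = 1 - Φ((t-d)/s); E[D|sel] = d + s φ((t-d)/s)/p
- either direction: p = 1 - Φ((t-d)/s) + Φ((-t-d)/s); E[D|sel] = d + s[φ((t-d)/s) - φ((t+d)/s)]/p

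Example, intensive arm, t = 1.0, either direction: p = 0.251 + 0.059 = 0.310, and E[D|sel] = 0.4 + 0.894(0.3185 - 0.1172)/0.310 = 0.981.

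**3. False difference on raw 12-month scores.** This is k x [(E[D|sel, intensive] - 0.4) - E[D|sel, standard]], with k = (r3,12 - r0,12)/0.8. Equal correlations give k = 0, so no bias. With 0.6/0.5/0.7, k = 0.2/0.8 = 0.25:

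| Selected | t | E[D] intensive | E[D] standard | Bracket | Bias (SD) | Share selected, standard / intensive |
|---|---|---|---|---|---|---|
| Either direction | 0.5 | 0.628 | 0 | 0.228 | +0.06 | 58% / 61% |
| | 1.0 | 0.981 | 0 | 0.581 | +0.15 | 26% / 31% |
| | 1.75 | 1.683 | 0 | 1.283 | +0.32 | 5% / 7% |
| Improvers only | 0.5 | 1.179 | 1.060 | -0.281 | -0.07 | 29% / 46% |
| | 1.0 | 1.534 | 1.449 | -0.315 | -0.08 | 13% / 25% |
| | 1.75 | 2.144 | 2.091 | -0.347 | -0.09 | 2.5% / 6.5% |

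**4. Change from enrolment** (an analysis the plan does not name). Here k = (r3,12 - r0,12 + 1 - 0.6)/0.8 = 0.5 or 0.75. Applied to the same brackets, this gives +0.11 to +0.96 SD (either direction) or -0.14 to -0.26 SD (improvers).

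**5. One five-option item** (latent normal cut at quintiles, trigger 1 to 3 options, simulated). The raw false difference is -0.30 to +0.18 options. On this coarse scale it is not zero even with equal correlations (-0.09 to -0.18 options).

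**6. Any of the 15 items.** In the same item model (visit correlation 0.6, no treatment effect, inter-item correlation 0 to 0.6), 99.5-100% of patients shift at least one option on some item and 89-99% shift at least two. Selection is then close to universal and its bias probably negligible.

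**7. Regression to the mean.** Standard arm, equal correlations, improvers at t = 1.0: E[D|sel] = 1.449. The slope of the enrolment score on D is (0.6 - 1)/0.8 = -0.5, so enrolment averages -0.72, month 3 +0.72 and month 12 0.00. The 0.72 SD gain from enrolment to month 12 arises with no treatment effect (about 1.05 SD at t = 1.75).

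**8. Numbers.** Under the planning mortality, survivors are 200 x 0.83 + 200 x 0.90 = 166 + 180 = 346. Taking survival as independent of selection, at t = 1.75 only about 22 (8.3 + 13.2) or 16 (4.1 + 11.7) would be re-measured. The standard error of the raw difference is then about √(1/8.3 + 1/13.2) = 0.44 SD or √(1/4.1 + 1/11.7) = 0.57 SD.

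**The case against.** The strongest reply is that no announced analysis is damaged. Aim (b) has no time point, both arms complete the form at enrolment and month 3, and Statistical analysis names no 12-month questionnaire comparison. The study calls itself preliminary and is sized on mortality. All of this stands, and it makes the concern conditional on a 12-month statement being made. It does not make the rule useful for such a statement.

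The second reply is that the bias may be nothing. That also stands: it is zero on raw normal scores with equal correlations, small at a 0.5 SD trigger, and probably negligible if a small shift on any item counts. At the strictest trigger the standard error exceeds the raw bias.

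Two stronger readings are tempting. A reader might infer that 12-month hypoglycemia frequency, aim (a), has the same gap, since the form covers "frequency of low glucose levels" and has two frequency items. The documents do not support this. The legend says "Clinical outcome at 12 months will also include frequency of hypoglycemia, analysed separately" and does not tie that outcome to the form; ambulance reports and nurse contacts are other visible routes, though the nurse schedule may not cover the standard arm. A reader might also infer that the subset says nothing about persistence. That is too strong: it can describe whether change persisted among patients who changed.

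**Conclusion.** The concern holds for any 12-month between-arm or durability statement on confidence or quality of life. Selection is on a post-randomisation change in that outcome, and nothing elsewhere in the plan corrects it. The month-3 comparison and mortality are untouched.

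Size and sign cannot be derived from the documents. Under the stated assumptions the raw false difference on a summary score lies between about -0.09 and +0.32 SD, and it could be negligible. The larger change-from-enrolment figures belong to an analysis the plan does not name. Because the trigger is undefined, a reader of the results could not correct for it. Severity is minor to should-fix.

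**What to change.** Delete the selection sentence in the Figure 4 legend and the matching main-text wording. Give the form at 12 months to every surviving randomised patient in both arms, by the same route where possible (for example post), returned so that the research nurse does not see it. Pre-specify an item or score, such as the quality-of-life item in Appendix 1, and compare the arms as randomised, adjusted for the enrolment response. Report deaths and non-response by arm, and state that the comparison is among survivors.

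The cost is at most about 346 forms before dropout. The additional number depends on the trigger: about 330 if the rule would have sent 16, about 140 if it would have sent 206 (0.5 SD, either direction: 95.6 + 110.3), and almost none if any one-option shift counted. Mailing, reminders and data entry follow, with likely non-response in the standard arm. That arm's single-contact wording must be reconciled with the month-3 and month-12 forms.

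A survivor limit remains. If survival correlates 0.2-0.5 with the 12-month score (assumed), deaths of 17% versus 10% shift the raw comparison by about -0.02 to -0.06 SD.

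If the rule is kept, define the score, threshold and direction of the trigger, limit the aim (b) conclusion to month 3, and label the 12-month answers as descriptive of patients who changed, with no between-arm or durability claim. That costs only wording, but gives up any such claim.

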**PI: [name]**

**Co-Investigators: [name], [name]**

**Statistical analysis: [name]**

## **Background**

Hypoglycemia is a common complication of diabetes treatment, particularly when glucose control is intensified (1-3). Until recently, hypoglycemia was regarded as an acceptable "side effect" of glucose lowering therapy, given the benefits of tight glycemic control at reducing microvascular, and to some extent macrovascular, complications of diabetes (2-7). However, studies in the past few years have demonstrated that hypoglycemia is probably a more serious side effect than initially thought (8-11). A major warning as to the potential dangers of hypoglycemia was delivered in the ACCORD study (12), when excess mortality was demonstrated in the intensive glucose arm of the trial, necessitating study termination and fuelling speculation about the role of intensive glucose control in the management of diabetes. The fear of hypoglycemia-induced death in diabetes is not unfounded as there are clear mechanistic pathways to explain this link. Hypoglycemia is associated with repolarisation abnormalities in the heart and increased thrombosis potential as we and others have shown (13-15). Indeed, large scale studies and anecdotal reports have shown associations between acute cardiac events/mortality and hypoglycemic events (11,16-18). Moreover, our preliminary data in Leeds have revealed that severe hypoglycemia, requiring emergency services intervention in 856 patients, is associated with 17.1% mortality within 12 months of the event (unpublished data). This death rate is comparable to diabetes patients sustaining acute cardiac ischemic event in Leeds, which currently stands at 15.8% (19). Also, the mean age of the diabetes cohort was only 61 years, and therefore the high death rate following hypoglycemia is certainly a major cause for concern (for gender and diabetes type distribution, see Figure 1). Moreover, our data showed that in excess of 200 individuals had recurrent severe hypoglycemic events, despite local pathways designed to ensure higher levels of clinical support. Interestingly, of the type 2 diabetes subjects, 28% were not on insulin, being managed with oral hypoglycemic agents (95% treated with sulphonylureas). The degree of documented hypoglycemia in this group was comparable to individuals on insulin therapy with glucose levels at the arrival of ambulance crew of  $1.8 \pm 1.1$  and  $1.9 \pm 0.7$  mmol/l, respectively ( $p > 0.1$ , unpublished data).

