### **Statistical analysis**

The observational part of the study will collect various data and will be the basis for future studies. Power calculations were based on the interventional study. Given our current data showing a death rate in excess of 17% within one year of hypoglycemia, we calculated that 200 individuals are needed in each of the study arms to detect a drop in mortality to 10% in intensively monitored patients (at  $p=0.05$ ). Between group analysis will be done using unpaired  $t$ -test for normally distributed data and the non-parametric Mann-Whitney test will be used for data that are not normally distributed. For categorical data, 2X2 contingency tables will be used and multiple regression analysis will be performed to determine potential causes of hypoglycemia.

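### The 12-month hypoglycemia comparison (aim 2a) takes no account of time alive and has no rule for deaths, so it is biased modestly against the intensive arm if counts are compared and mortality falls as the trial is designed to detect

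*Combined protocol and SAP*

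**What the plan says.** The Aims section gives the purpose of the interventional study as to "investigate the effect of regular glucose monitoring and specialist nurse input into a) future hypoglycemic events", followed by confidence and quality of life, and by clinical outcome. The legend to Figure 4, in the Interventional study section, fixes the time point: "Clinical outcome at 12 months will also include frequency of hypoglycemia, analysed separately". Neither place says whether frequency means a count, a rate or the occurrence of any event.

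The Statistical analysis section names an unpaired t-test for normally distributed data, and says that the "non-parametric Mann-Whitney test will be used for data that are not normally distributed". Categorical data go into 2x2 tables. Multiple regression is reserved for potential causes of hypoglycemia. There is no mention of time at risk, censoring, or how a patient who dies during the year enters the comparison.

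The same section bases the sample size on death: "Given our current data showing a death rate in excess of 17% within one year of hypoglycemia", it states that "200 individuals are needed in each of the study arms" to "detect a drop in mortality to 10% in intensively monitored patients". The Background gives the source of the control figure: in the local cohort of 856 patients, severe hypoglycemia "is associated with 17.1% mortality within 12 months of the event (unpublished data)".

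**The concern.** A patient who dies in month 2 without a further event has had little time in which to have one. In a Mann-Whitney test on raw counts that patient ranks among the best outcomes, and in a 2x2 table the patient counts as event-free. If deaths are left out instead, the groups compared are survivors selected after randomisation. Randomisation does not protect either comparison, because the difference in survival arises after it.

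The design scenario is one in which survival differs between arms. The patients whose deaths are prevented stay at risk for the full year and may have further events, all of which are counted in the intensive arm. A gain on mortality would then take something away from the result on aim 2a. Conversely, an arm with more deaths would appear to have less hypoglycemia.

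**Working it through.** **Inputs from the protocol.** Control mortality 17.1% (Background; the Statistical analysis section says over 17%), intensive-arm mortality 10% (the effect to be detected), 200 patients per arm. Expected deaths at these values: 0.171 × 200 = 34.2 and 0.10 × 200 = 20.

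The figure of 200 per arm is itself not reproduced at conventional power. For 17% versus 10%, two-sided 0.05, 80% power needs 373 per arm, and 200 per arm gives 54%. The plan states no power. That is a separate matter and does not affect what follows.

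**Assumptions, since the protocol gives no figures.**
- Let k be the event rate of patients who would die under standard care, relative to the rest (rate 1). I take k = 0.5, 1 and 3.
- Let e be the mean fraction of the year lived by those who die. I take 0.5 (deaths spread evenly) and 0.25 (earlier deaths).
- There is no true effect of the intervention on the event rate.
- In the intensive arm, 0.171 − 0.10 = 0.071 of patients are saved and live the full year.

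**Expected events per randomised patient.**
- Control: 0.829 + 0.171 × k × e
- Intensive: 0.829 + 0.071 × k + 0.10 × k × e

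**Ratio of raw counts, intensive to control.**
- k = 1, e = 0.5: 0.950 / 0.9145 = 1.039
- k = 1, e = 0.25: 0.925 / 0.87175 = 1.061
- k = 3, e = 0.5: 1.192 / 1.0855 = 1.098
- k = 3, e = 0.25: 1.117 / 0.95725 = 1.167
- k = 0.5: 0.8895 / 0.87175 = 1.020 (e = 0.5) and 0.877 / 0.850375 = 1.031 (e = 0.25)

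Any-event proportions move similarly. With a common event rate of 0.25 to 2 per year and constant hazards giving 17% versus 10% deaths, the ratio of proportions is 1.03 to 1.04.

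**Survivors only.** Ratio = (0.829 + 0.071 × k) / 0.90, which is 1.000 at k = 1, 1.158 at k = 3 and 0.961 at k = 0.5.

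**Events per patient-year alive.** Divide the control count by 0.829 + 0.171 × e and the intensive count by 0.90 + 0.10 × e. The ratio is 1.000 at k = 1; 1.057 (e = 0.5) or 1.100 (e = 0.25) at k = 3; and 0.98 or 0.97 at k = 0.5.

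**Effect on a true 20% reduction (rate ratio 0.80).**
- k = 1: raw counts show 0.80 × 1.039 = 0.831 or 0.80 × 1.061 = 0.849, an apparent reduction of about 17% or 15%.
- k = 3: raw counts show 0.878 or 0.934, about 12% or 7%; survivors only, 0.926.

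**When the point estimate changes sign.** The true reduction must be smaller than 1 − 1/ratio. For raw counts that is about 4% to 6% at k = 1 and about 9% to 14% at k = 3.

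**Test behaviour.** I simulated 200 per arm, 17% versus 10% deaths, over-dispersed counts with an assumed mean of one event per year, and no true effect. At k = 1 the t-test on raw counts rejects in 5.9% of runs and Mann-Whitney in 6.0%. At k = 3 the figures are 8.1% and 6.5%, and the t-test in survivors only rejects in 13.1%. A true rate ratio of 0.70 appears as 0.73 at k = 1, and at k = 3 as 0.77 (all patients) or 0.82 (survivors only).

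**The case against.** **The plan is silent; it does not rule out a sound analysis.** A reader might infer that the plan has chosen to ignore death. The text does not go that far. Frequency could be analysed as a rate, and the Figure 4 drawing is not available to us, although its legend is. The Appendix 1 question on how often attacks occur has rate-like answers (monthly, weekly, daily) that a shorter life does not lower mechanically. This stands in part. Still, none of the named tests takes an offset, and a t-test on individual rates is unstable for early deaths. The questionnaire is repeated at 12 months only in selected patients, and the dead cannot answer it, so that route leads to a survivors-only comparison.

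**The 10% is a target.** A reader might infer that the plan expects 17% versus 10% to die. It gives 10% as the effect to detect, in a study it calls preliminary. This objection stands: with equal mortality there is no differential.

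**The larger figures rest on an assumption.** The Background says it is unclear whether low glucose contributes to death or whether severe hypoglycemia occurs more in terminally ill patients. Either explanation would link dying with more hypoglycemia, but carrying that over to recurrent events within this cohort is inference. At k = 0.5 the survivors-only and person-time biases change direction, while the raw-count bias stays at 2% to 3% against the intensive arm.

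**The bias rarely misleads outright.** In simulations with a true 20% reduction, assumed means of 0.5, 1 or 3 events per year and k = 1 or 3, a significant Mann-Whitney result against the intensive arm occurred in at most about 0.5% of runs. This also stands: the damage is dilution and lost power.

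**Conclusion.** The point holds in conditional form. If counts or any-event proportions are compared with the named tests, and mortality falls as the trial is designed to detect, aim 2a is biased against the intensive arm. For counts the size is about 4% to 6% at equal event rates, which rests only on the design mortality and the assumed timing of deaths. It is about 10% to 17% if patients destined to die are assumed to have three times the event rate, a value the protocol does not supply.

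The tempting stronger conclusion is that saving lives will make the intensive arm look worse on hypoglycemia. The documents do not support it. A reversed point estimate needs a true benefit below about 4% to 6% at equal rates, or 9% to 14% at threefold rates.

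This is nevertheless more than a missing detail, because the named tests perform worst under the trial's own design scenario and a better analysis is readily available. It should be changed.

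**What to change.** In the Statistical analysis section:

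1. Define the aim 2a outcome as the number of severe, ambulance-reported hypoglycemic events from randomisation to death or 12 months. Compare arms by negative binomial regression with log time alive as offset, including all randomised patients.
2. Show deaths by arm in the same table.
3. Report the proportion with a further severe event or death by 12 months as a supporting analysis, so that a gain in survival cannot count against the intervention.
4. Label 12-month laboratory values (HbA1c, albumin/creatinine ratio) as values among survivors.

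The cost is wording and a little extra analysis. The main analysis needs event counts and dates of death; death is already the sample-size outcome, and the ambulance pathway in the Plan of investigation already reports severe events. Restricting the outcome to those events matters because the questionnaire records other episodes only in categories, and the standard arm is contacted only once by the nurse.

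There are two downsides. The offset removes the bias fully only when event rates are equal: at a threefold rate 5.7% to 10% remains, and at half the rate 2% to 3% remains in the other direction. The composite mixes in deaths unrelated to glucose and answers a different question from aim 2a, so it should stay supporting.
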